
 • To demonstrate the efficacy of active study vaccine in the prevention of RT-PCR-confirmed RSV-mediated LRTD during the second year when compared to placebo in adults aged 60 years and above 	
 • First occurrence of RT-PCR-confirmed RSV-mediated LRTD during the second year, with onset after study Day 365

 • To demonstrate the efficacy of active study vaccine in the prevention of any RT-PCR-confirmed RSV-mediated ARI during the second year when compared to placebo 	
 • First occurrence of any RT-PCR-confirmed RSV-mediated ARI during the second year, with onset after study Day 365

Objectives	Endpoints

 To demonstrate the efficacy of active study vaccine in the prevention of predefined clinically relevant disease associated with RT-PCR-confirmed RSV-mediated ARI over the whole study when compared to placebo 	
 First occurrence of predefined clinically relevant disease associated with RT-PCR-confirmed RSV-mediated ARI over the whole study with onset at least 14 days after dosing of study vaccine
NON-CONFIRMATORY SECONDARY	

 To evaluate safety in terms of serious adverse events (SAEs) and adverse events of special interest (AESIs) until 6 months after vaccination 	
 Occurrence and relationship of vaccination to SAEs and AESIs until 6 months after vaccination

 In the Safety Subset and in subgroups of the Safety Subset (including but not limited to participants at increased risk of severe RSV disease), to evaluate the safety and reactogenicity in terms of solicited local and systemic adverse events (AEs) during 7 days after vaccination, and in terms of unsolicited AEs during 28 days after vaccination 	
 Occurrence, intensity, duration and relationship to vaccination of solicited local and systemic AEs during 7 days after vaccination and of unsolicited AEs during 28 days after vaccination

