The blood samples that are collected between 2 and 4 days after symptom onset (ARI Day 3-5) from participants with an RSV, hMPV, or influenza-mediated ARI episode will be assayed by serology (which may include pre-F/post-F enzyme-linked immunosorbent assay (ELISA) and RSV virus neutralizing antibodies [VNA], as available and applicable) to assess immune responses and correlates that are associated with RSV infection. The samples will also be used for exploration of biomarkers that correlate with RSV infection and RSV disease severity (which may include RT-PCR for RSV, ribonucleic acid [RNA] transcriptomics to assess gene regulation [clusters] and expression patterns, cytokine/chemokine-dependent immunophenotyping, and immune repertoire analysis, as available and applicable).

SAFETY EVALUATIONS

For All Participants

All (S)AEs and special reporting situations related to study procedures or to non-investigational (concomitant) Janssen products will be collected from informed consent form (ICF) signature onwards until the end of the study for all participants. All other SAEs and AESIs will be collected from administration of study vaccine (Day 1) until 6 months after vaccination. AEs leading to discontinuation from the study will be collected for the duration of the study. All COVID-19 cases will be collected for all participants for the duration of the study.

ARIs and complications related to RSV, hMPV, and influenza-mediated ARIs that classify as SAE will be captured in all participants and reported as SAEs in the eCRF continuously from the time of vaccination until 24 months after vaccination.

All participants will be closely observed for a minimum of 15 minutes after vaccination to monitor for the development of any acute reactogenicity. This post-vaccination observation period should be extended for participants whom in the investigator's opinion would require further observation or for any occurrence of a localized reaction or (minor) systemic symptoms during the post-vaccination observation that require monitoring for any progression.

Vital signs will be collected prior to vaccination for all participants. At non-vaccination visits, vital signs will be measured if deemed necessary by the investigator.

For Participants in the Safety Subset

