6.1.2. Phase Definitions

The phases in the study will be constructed as follows:

Table 4: Phase Definitions

Phase	Phase #	Period	Period #	Interval	
				From	To
Screening	1			Date and time of signing the informed consent form	One minute prior to start of post dose period
Regimen	2	Post-Dose	1	Date and time of vaccination	Minimum of:

Table 4: Phase Definitions

Phase	Phase #	Period	Period #	Interval	
				From	To
					a) 23:59 at the date of last contact (for early study discontinuation) b) 23:59 at the database cut-off date in case of interim analysis c) Maximum (28 days after vaccination at 23:59, scheduled visit 4 weeks after vaccination at 23:59)
First Year Follow up	3			One minute after Post-Dose period end	Minimum of: a) 23:59 at the date of last contact (for early study discontinuation) b) 23:59 at the database cut-off date in case of interim analysis c) One minute prior to Second Year Follow up
Second Year Follow up	4			00:00 at the date of the Month 12 visit *	Minimum of: a) 23:59 at the date of last contact (for early discontinuation or participants that completed the study) b) 23:59 at the database cut-off date for analyses conducted before the final analysis.

The combination of 'Post-Dose' period and 'First Year Follow up' period will be referred as 'First Year'. The combination of the 'Regimen', 'First Year Follow up' and 'Second Year Follow up' periods will be referred as 'Whole Study' phase.

*If Month 12 visit not available, and there are ARI surveillance questions available after the relative day 365, then the relative day 365 (vaccination date + 365) will be used as the start of the Second Year Follow up.

'Month 12' and 'Day 365' visit are used interchangeably in the rest of the document.

For the potential adverse events of special interest (AESI) analysis the following intervals will also be used:

Table 5: Interval Definition for potential AESI analysis

Dose	Interval	Interval	
		From	To
Post-vaccination	0 - 28 days post-dose	Date time of vaccination	Min of: 
 • 23:59 at date of last contact (for discontinuations) • 23:59 at the database cut-off date in case of interim analysis • Maximum (date of vaccination + 28 days at 23:59, date of scheduled visit 4 weeks after vaccination at 23:59)
	29 - 56 days post-dose*	One minute after the end of the interval '0 - 28 days post-dose'	Min of: 
 • 23:59 at date of last contact (for discontinuations)

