			
 • 23:59 at the database cut-off date in case of interim analysis • Date of vaccination + 56 days, at 23:59
	57 days - 6 months post-dose	One minute after the end of the interval '29 - 56 days post-dose'	Min of: 
 • 23:59 at date of last contact (for discontinuations) • 23:59 at the database cut-off date in case of interim analysis • Maximum (Date of vaccination + 169 days at 23:59 , date of scheduled visit 169 days post vaccination at 23:59)
	> 6 months post-dose	One minute after the end of the interval '0 - 6 months post-dose'	Min of: 
 • 23:59 at the date of last contact (for discontinuations/ completions) • 23:59 at the date of DB cut-off for interim analyses

The combination of the '0 - 28 days post-dose' interval and the '29 - 56 days post-dose' interval will be referred as '0 - 56 days post-dose'. The combination of the '0 - 28 days post-dose', '29 - 56 days post-dose' and '57 days - 6 months post-dose' intervals will be referred as '0-6 months post-dose'.

*In case the '0 - 28 days post-dose' interval end later than 56 days post vaccination then the '29 - 56 days post-dose' interval is not required.

For example, if a participant had Day 29 visit at relative day 57, then the following intervals will be created:

- 0 - 28 days post-dose, lasting from 0 to relative day 57,
- 57 days - 6 months post-dose, lasting from 58 onwards.

The same logic will apply for all intervals that end later after the next interval.

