6.7.1.1.2. Analysis of Adverse Events

Number and percentage of participants with at least one particular AE (unsolicited/solicited) will be tabulated. Unsolicited AEs will be summarized by System Organ Class and Preferred Term. Solicited AEs will be summarized by class (administration site, systemic) and preferred term. AESI analyses will be summarized by Interest Category and Preferred Term.

For solicited AEs following tables will be provided: summary, by worst severity grade, at least grade 3, related (systemic only), time to onset (in days) and duration (in days). Note: Duration is defined as number of days from the start of the event until resolution of the event. The time to first onset is defined as (date of first onset – reference date + 1). The reference date is the start date of the post dose period.

For unsolicited AEs following tables will be provided: summary table (including SAE, fatal outcome and vaccination discontinuation), all events, at least grade 3, permanent stop of vaccine and related. For SAEs following tables will be provided: all events, all related events, events with fatal outcome and related events with fatal outcome.

Moreover, tables with Covid AEs, potential AESI as identified by the investigator, potential AESIs selected programmatically and potential AESI qualified for assessment will be created.

Potential AESIs selected programmatically will be tabulated by categories: ‘Embolic and thrombotic events (SMQ)’ and ‘Haematopoietic Thrombocytopenia (SMQ) (broad) or HLT = Thrombocytopenias’. Potential AESI determined programmatically, related to study vaccine (investigator assessment), will be tabulated similarly.

Potential AESIs as identified by the investigator, will be tabulated by categories: ‘Embolic and thrombotic events (SMQ)’ and ‘Haematopoietic Thrombocytopenia (SMQ) (broad) or HLT = Thrombocytopenias’, and ‘Other’. Potential AESI as identified by the investigator, related to study vaccine (investigator assessment), will be tabulated similarly.

Potential AESIs qualified for assessment will be tabulated by categories: ‘Embolic and thrombotic events (SMQ)’ and ‘Haematopoietic Thrombocytopenia (SMQ) (broad) or HLT=Thrombocytopenias’.

All potential AESI analyses will be presented by phase as well as by time interval. The definition of the different time intervals can be found in Section 6.1.2.

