6.10.2. Safety Analyses

SAE analyses will also be presented by time interval. The definition of the different time intervals can be found in Section 6.1.2.

AEs of interest and AEs of (Clinical) interest are also defined and will be tabulated.

Additionally, the following analyses will be added per FDA request:

- immediate reactions will be tabulated by worst severity grade
- the number of events in addition to the number of participants, already presented, will be tabulated for unsolicited AEs, SAEs and AEs of (special) interest.

Immediate reactions:

All solicited AE tables are based on the overall assessment by principal investigator, extracted from the investigator assessment pages (which spans the evaluation period since vaccination) of the CRF.

In response to FDA comments, immediate reactions should also be tabulated. Therefore, on top of the solicited AE tables based on the overall assessment by the principal investigator, a table by worst severity grade will be created focusing on the 15- or 30-minute on-site assessment post vaccination. In China the on-site assessment was planned at 30 minutes post-vaccination, in all other countries it was planned at 15 minutes post vaccination.

Note that for Erythema and Swelling the grades for immediate reactions are only captured in the FA domain with a diameter. The grades should be derived from the diameter as indicated below, grade 4 is not determined as this is not based on the diameter.

Table 13: Grades for erythema and swelling based on diameter

Diameter	Grade
25-50 mm	Grade 1
>50-100 mm	Grade 2
>100 mm	Grade 3

The 15- or 30-minute on-site assessment for pyrexia is only captured in the vital signs domain, grades should be based on the temperature captured as indicated in the table below:

Table 14: Grades for pyrexia based on temperatures

Temperature (°C)	Temperature (°F)	Grade
38.0-38.4°C	100.4-101.1°F	Grade 1
38.5-38.9°C	101.2-102.0°F	Grade 2
39.0-40.0°C	102.1-104.0°F	Grade 3
>40.0°C	>104.0°F	Grade 4

Counting the Number of Events

When counting the number of events, overlapping/consecutive events that are combined into one AE according to section 6.7.1.1.3 are counted as one event. The number of events will only be shown for subset of tables.

Adverse Events of Interest and Adverse Events of Clinical Interest

The below table provides the AEs of (clinical) interest and their selection criterium.

Table 15: Adverse Events of (clinical) interest

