6.11. Discontinuation of the study

On the 29th of March 2023 the EVERGREEN study was permanently terminated. All participants are to be followed up for 6 months post vaccinations for safety collection. ARIs will not be collected after the 29th of March 2023 or followed up.

Due to the early termination of the study, the Sponsor decided not to perform the complete planned analysis as described in the protocol and SAP. The final analysis will contain the following:

- Efficacy analysis for secondary endpoints and for a limited selection of the exploratory endpoints.
- Safety analysis presented only per period (as defined in [Table 4](#)).
- Immunogenicity analysis of all completed assays in the database at the time of the analysis.

Moreover, no local specific cohort analysis will be conducted.

The following efficacy endpoints will be analyzed per year and over the whole study:

- First occurrence of any RT-PCR-confirmed RSV-mediated LRTD and ARI
- First occurrence of any RT-PCR-confirmed RSV-mediated LRTD and ARI by subtype
- First occurrence of any clinically relevant diseases associated with RT-PCR-confirmed RSV-mediated LRTD and ARI
- AUC for participants with any RT-PCR-confirmed RSV-mediated LRTD and ARI
- Viral loads

Note: In the cases that an RSV ARI is ongoing during the time of the discontinuation and does not have an end date, the 29th of March 2023 will be used as an ARI end date. An ARI with no end date will be considered as an RSV ARI, if an RSV positive result is available within 15 days after the ARI onset.

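### SAP 6.11 drops the 0-6 month interval tables from the final safety analysis, so the secondary endpoint of SAEs and AESIs to 6 months is reported only inside the first-year periods and not as its own window

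*SAP*

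**What the plan says.** - **Endpoint.** The protocol (Synopsis and Section 3) lists as a non-confirmatory secondary endpoint "Occurrence and relationship of vaccination to SAEs and AESIs until 6 months after vaccination".
- **Collection.** The Synopsis says "All other SAEs and AESIs will be collected from administration of study vaccine (Day 1) until 6 months after vaccination"; Section 8.4 agrees. SAP 6.11 keeps this 6-month safety follow-up for every participant after the termination of 29 March 2023.
- **Planned outputs.** SAP 6.7.1.1.2: "All potential AESI analyses will be presented by phase as well as by time interval". SAP 6.10.2: "SAE analyses will also be presented by time interval". Both point to the intervals in SAP 6.1.2 (Table 5), where a combined 0-6 months interval is defined.
- **Final analysis.** SAP 6.11: "Safety analysis presented only per period", with a reference to Table 4.
- **Table 4.** Post-Dose runs to 28 days after vaccination or the 4-week visit, if later. First Year Follow up runs until just before Second Year Follow up, which starts at "00:00 at the date of the Month 12 visit". The only combinations defined are First Year and Whole Study.

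**The concern.** The endpoint has a fixed time limit, and the study continues after termination so that each participant's 6 months of safety follow-up is completed. The final analysis then has no table that stops at 6 months.

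The nearest substitute is the first-year output, which has two weaknesses. After 6 months only some kinds of SAE are still collected, so the block joins general SAE capture to selective capture. If Post-Dose and First Year Follow up are shown separately, a reader cannot rebuild the 0-6 month number of participants with an event, because someone with events in both periods is counted in each.

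SAP Table 1 shows that version 4.0 added both Section 6.10, with the SAE interval tables, and Section 6.11, with the restriction. The version therefore adds a set of tables and, read literally, excludes them from the final analysis. Neither 6.11 nor Appendix 2 (changes to protocol-planned analyses) says what this does to the 6-month endpoint.

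**Working it through.** The plan gives no figure to reproduce. The check sets the period boundaries against the endpoint window. SAP 6.1.1 defines Study Day as visit date minus vaccination date plus 1, so vaccination + 28 days is Day 29. The Month 12 visit is taken at its nominal Day 365.

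**1. Table 4 against the endpoint**

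| Block | Study Days (nominal) | Ends at 6 months? |
|---|---|---|
| Post-Dose | 1 to 29 | No |
| First Year Follow up | 30 to 364 | No |
| First Year (combined) | 1 to 364 | No |
| Endpoint (protocol Month 6) | 1 to 182 | n/a |

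First Year Follow up lasts 364 − 30 + 1 = 335 days. The part up to Day 182 is 182 − 30 + 1 = 153 days, or 153/335 = 46%. The 6-month point falls inside this period.

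**2. Are the 0-6 month events lost?** No. SAP 6.7.1.1.3 allocates events by start date. Days 1-182 lie wholly within Days 1-364, so every SAE or AESI in the endpoint window appears in Post-Dose or First Year Follow up.

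**3. What else can enter the first-year block after 6 months?**
- AESIs: collection ends at 6 months, so almost nothing beyond spontaneous late reports.
- SAEs related to study procedures or to concomitant sponsor products: collected to study end (Synopsis; 8.4).
- ARI-related SAEs: the Synopsis and 8.4 report them to 24 months; footnote l of Protocol 1.3.2 says 6 months. RSV-confirmed ARIs are excluded from AE analyses (SAP 6.7.1.1.1), which leaves non-RSV ARIs. ARI collection stopped on 29 March 2023 (SAP 6.11).

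**4. Can the two periods be added?** Not as participant counts. SAP 6.7.1.1.2 counts participants with at least one event, and SAP 6.7 uses participants in the phase as the denominator. The combined First Year block would count each person once, if it is produced, but would still include the later SAEs in step 3.

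**5. Can Table 5 be restored as it stands?** Apart from early last contact or an interim cut-off, its 6-month interval ends at "Maximum (Date of vaccination + 169 days at 23:59 , date of scheduled visit 169 days post vaccination at 23:59". Vaccination + 169 days is Study Day 170. The Day 169 visit is for the Immuno Subset only (Protocol 1.3.1, Visit 2c), so for most participants Day 170 is the cut-off.
- Protocol Month 6 is Day 182 (−7/+14), that is, Days 175 to 196.
- Gap to the nominal day: 182 − 170 = 12 days.
- Gap to the visit window: 175 − 170 = 5 to 196 − 170 = 26 days.

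**The case against.** The strongest reply is that nothing reportable disappears. Events in months 0-6 are all in the first-year output. For AESIs, first-year counts are in practice the 6-month counts. The later SAEs are a narrow residue. The endpoint is descriptive and untested, and 6.11 openly states that a terminated study gets a reduced analysis. It restricts only the final analysis, and Protocol 9.5.1 also has safety analysed at the primary analysis. Table specifications sit in separate documents, so 6.11 may not have been meant to cancel 6.10.2.

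Most of this stands and limits the point. Four stronger readings are tempting and are not supported:

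- **The endpoint is not tabulated.** Step 2 of the working shows that its events are.
- **Half the first-year result is affected**, since about half the year lies after Day 182. That counts calendar days. SAP 6.7 uses participants per phase, not person-time, as the denominator, so months with little collection do not dilute the percentages.
- **Only the final analysis holds complete 6-month data.** 29 March 2023 minus 182 days is 28 September 2022, so anyone vaccinated after about then was short of 6 months at termination. Footnote b of Protocol 1.3.1 provides for late enrolment, but no last vaccination date or number is given, so this is a possibility and not a finding.
- **The interval tables are already programmed.** Neither document says so.

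What the reply does not answer is that 6.11 says only, gives the endpoint no table of its own, and conflicts with 6.7.1.1.2 and 6.10.2 without explanation.

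**Conclusion.** The point holds as a reporting gap. As written, the final analysis gives the 6-month SAE/AESI endpoint only within first-year blocks. The effect is small for AESIs. For SAEs it is the inclusion of selectively collected later events and, where the periods are shown separately, counts that cannot be combined. The documents hold no event counts, so the number of SAEs or participants involved cannot be stated.

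This rests on three assumptions: that the restriction in 6.11 is meant literally, that the separate table specifications do not already keep a 0-6 month table, and that Month 6 means the protocol's Day 182. The change is worth making because it is cheap and makes the final report match the stated endpoint. It does not call the safety data themselves into question.

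**What to change.** 1. In SAP 6.11, replace the restriction with: *per period (Table 4) and, for SAEs, potential AESIs and fatal events, also cumulatively from vaccination to 6 months, by vaccine group.*
2. Name that cumulative table as the analysis of the secondary safety endpoint, and show later-onset events separately, labelled as selectively collected.
3. Do not carry over the Table 5 cut-off unchanged. Reconcile vaccination + 169 days with the protocol's Month 6 (Day 182, −7/+14 days), so that the last days of the endpoint window are not left out, and state how onsets up to a contact as late as Day 196 are handled.
4. Reconcile the reporting period for ARI-related SAEs: footnote l of Protocol 1.3.2 says 6 months, the Synopsis and Section 8.4 say 24 months. The answer determines what can appear among the later events.
5. Make 6.7.1.1.2 and 6.10.2 consistent with 6.11, and record the change in Appendix 2.

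The cost is SAP wording and a few extra descriptive tables. No new data collection is needed.

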7. SUPPORTING DOCUMENTATION

7.1. Appendix 1 List of Abbreviations

ADaM	Analysis Data Model
AE	adverse event
AESI	adverse event of special interest
ATC	anatomic and therapeutic class
BCC	Brighton Collaboration Case Definition
BMI	body mass index
CD4	cluster of differentiation 4
CD8	cluster of differentiation 8
CDC	Center for Disease Control and Prevention
CEC	Clinical Event Adjudication Committee
CI	confidence interval
CRF	case report form
CTP	clinical trial protocol
IDMC	Independent Data Monitoring Committee
ECG	electrocardiogram
ELISA	enzyme-linked immunosorbent assay
ELISpot	enzyme-linked immunospot
FAS	full analysis set
FDA	Food and Drug Administration
FEV1	forced expiratory volume in 1 second
FEV6	forced expiratory volume in 6 second
FVC	forced vital capacity
GMC	geometric mean antibody concentration
GMT	Geometric Mean Titre
HR	hazard ratio
HLT	higher level term
ICF	informed consent form
ICS	intracellular cytokine staining
IFN γ	interferon gamma
IL2	interleukin 2
IRR	incidence rate ratio
ITT	intent-to-treat
LLOQ	lower limit of quantification
LOD	lower limit of detection
NA	not applicable
PBMC	peripheral blood mononuclear cells
PPE	per protocol efficacy analysis set
PPI	per protocol immunogenicity analysis set
PRAC	Pharmacovigilance Risk Assessment Committee
SAE	serious adverse event
SAP	Statistical Analysis Plan
SD	standard deviation
SDTM	Study Data Tabulation Model
SE	standard error
SFU	spot forming units
SMQ	Standardised MedDRA Queries
TNF α	tumor necrosis factor alpha
ULOQ	upper limit of quantification
VE	vaccine efficacy
VNA	virus neutralizing antibody
VTE	Venousthromboembolism
WHO	World Health Organization

